COVER PAGE

TITLE: Vaginal Estrogen and Pelvic Floor Physical Therapy in Women with Symptomatic Mild Prolapse

NCT01648751

September 2016

SPECIFIC AIMS

Pelvic organ prolapse (POP) is a common disorder among women. It has been estimated that 200,000 women in the United States undergo inpatient procedures to repair pelvic floor disorders each year, and by the year 2030, over 7 million surgeries will be performed annually. Women have an 11% lifetime risk of undergoing surgery for pelvic floor disorders, and a 30% risk for re-operation. Vaginal birth is considered a major risk factor since most parous women have mild asymptomatic prolapse. However, the factors that lead to prolapse progression and symptom development are not clear. Currently, there is a lack of research correlating patient symptoms and degree of prolapse with biochemical data, such as collagen content and collagenase activity. POP has traditionally been managed either conservatively, with a pessary, or through surgical intervention. Recent studies suggest that Pelvic Floor Physical Therapy (PFPT) may also be beneficial. The role of vaginal estrogen is unclear, and to date, limited data exist on its use in the treatment of prolapse.

Prior studies in our lab confirm that the degradation of the pelvic connective tissues is regulated by estrogen and progesterone. Data from animal models suggest that hormones given to women with normal support or with mild prolapse will prevent vaginal connective tissue breakdown and preserve mechanical integrity. Currently, it is our clinical practice to offer patients with symptomatic mild pelvic organ prolapse conservative treatment with pelvic floor physical therapy (PFPT) and vaginal estrogen. We hypothesize that restoration of the vaginal support complex through re-alignment and muscle strengthening by way of PFPT, and improved tissue integrity through the use of vaginally delivered hormones, will lead to decreased symptoms and improved patient satisfaction with her treatment outcome. We propose to test this hypothesis in a randomized trial in which women with symptomatic mild prolapse (stage I-III) who have opted to undergo PFPT, receive treatment with PFPT in combination with vaginal estrogen versus placebo. Ultimately, we hope to use this data as a foundation for instituting a larger trial in which prolapse progression strategies are tested in women with mild to moderate prolapse.

Aim 1: To determine the impact of vaginally delivered estrogen on global impression of improvement in women with symptomatic stage I-III pelvic organ prolapse who are undergoing pelvic floor physical therapy. Women will be randomized to PFPT in combination with vaginal estrogen versus placebo, and will be administered questionnaires at baseline and 6 months after treatment. The primary outcome is global impression of her improvement, measured via administration of the validated Patient Global Impression of Improvement questionnaire (PGI-I).¹⁰ Other validated questionnaires will be used to assess symptoms, sexual function, and guality of life. Results will be compared between groups.

Aim 2: To determine the impact of vaginal estrogen on POP stage, as measured by the Pelvic Organ Prolapse Quantification (POP-Q) exam. The POP-Q exam is an objective validated clinical tool that is used to assess prolapse stage.¹¹ POP-Q exam will be performed at baseline and 6 months after treatment.

Aim 3: To evaluate the effect of PFPT and vaginal estrogen on biomarkers of prolapse, and to correlate this data with patient symptoms and anatomical changes. Vaginal tissue swabs will be collected at baseline and 6 months. Collagenase activity will be analyzed.

BACKGROUND

Estrogen receptors are present throughout the female pelvic floor and have been detected in the levator ani muscles and urogenital ligaments. This biological finding provides a basis for the suggestion that estrogen may play a role in the development of pelvic organ prolapse, and in turn, may be beneficial in the prevention and treatment of this condition. Several studies have confirmed that the degradation of pelvic connective tissues is regulated by hormones. In primates, estradiol given to ovariectomized animals increased collagen synthesis and the expression of vaginal cystatin C, an inhibitor of collagen proteases. In human studies, biopsy specimens of the arcus tendineous fasciae pelvis in postmenopausal women who were not on hormones showed a decrease in type I collagen and collagen ratios compared to biopsies from premenopausal women, whereas no decrease was found in postmenopausal women who were on hormone therapy. 16

Additional studies on human tissue and in rats also suggest that hormones may have a protective effect against supportive tissue degradation^{8,9} and may lead to restoration of biomechanical properties.¹⁷

To date, limited data exist from randomized controlled trials and the role estrogen in the prevention and treatment of prolapse remains unclear. One small randomized placebo-controlled trial compared the effects of raloxifene, tamoxifen, and oral conjugated equine estrogen (CEE) on the pelvic floor, and was part of a larger osteoporosis trial. The patients were taught Kegel exercises and encouraged to perform home exercises daily, but did not undergo formal pelvic floor physical therapy. Patients with prior hysterectomy were excluded, but those using pessaries were not. In this trial, 2 of 8 patients in the oral CEE group demonstrated worsening prolapse, and 2 or 8 showed an improvement. More evidence is needed to determine the impact of estrogen and pelvic floor muscle exercises on the treatment and possibly prevention of pelvic organ prolapse.

We believe that the optimal approach to improving prolapse symptoms in the patient with mild prolapse requires both re-alignment and strengthening of the levator muscles via pelvic floor physical therapy (PFPT), and optimization of tissue integrity via local estrogen therapy. Although recent studies suggest a reduction in prolpase symptoms with PFPT,^{5,6} the impact of complementary therapy with vaginally delivered hormones remains unknown. It is our current clinical practice to offer patients with mild symptomatic pelvic organ prolapse conservative treatment with PFPT and vaginal estrogen. We do not suggest this treatment regimen for women with more severe prolapse, as we believe that it will have little clinical benefit. In the proposed trial, we plan to evaluate the effect of vaginal estrogen on the treatment of symptomatic mild prolapse with PFPT.

SIGNIFICANCE

The estimated annual direct cost for pelvic organ prolapse surgery is over \$1 billion dollars. ¹⁹ As the population ages and the demand for care of pelvic floor disorders increases, ²⁰ it is critical that we investigate alternatives to surgical intervention and develop new strategies for prevention. To date, few studies have compared the effectiveness of our current treatments for mild prolapse. Thus, it is difficult to counsel women on their risk for prolapse progression or whether a specific treatment is beneficial. This study provides a unique opportunity to explore a commonly prescribed treatment alternative to pessaries and surgery for patients with mild symptomatic prolapse, and to correlate patient symptoms and anatomical findings with biochemical data. We believe that the results of this study will improve our comprehension of the disease mechanism of prolapse, and will have future implications for averting or delaying disease progression. Moreover, this study will serve as critical content for a future larger study in which we compare the effectiveness of therapies for mild prolapse.

RESEARCH DESIGN AND METHODS

Overview: This is a randomized placebo-controlled trial in which women with symptomatic mild prolapse who have opted to undergo Pelvic Floor Physical Therapy (PFPT), receive treatment with PFPT in combination with vaginal estrogen versus placebo. Patients will be followed for a 6-month timeframe. This study has been approved by the University of Pittsburgh Institutional Review Board.

Study Location: Patient recruitment and exams will take place at the Women's Center for Bladder and Pelvic Health at Magee-Womens Hospital, which is part of the University of Pittsburgh Medical Center (UPMC). Additional recruitment sites at Magee include: the Midlife Health Center and Western PA Women's Healthcare Associates. Pelvic Floor Physical Therapy will take place at UPMC Centers for Rehab Services. Biochemical analysis of the vaginal swabs will take place at the Magee-Womens Research Institute in [name] laboratory.

Sample size: Given the lack of data on PFPT and vaginal estrogen in the treatment of prolapse, the decision was made to conduct a pilot study, with plans to use this data as a foundation for instituting a larger clinical trial in the future. A convenience sample size of 53 patients (27 in the treatment group and 26 controls) was chosen to comply with the budget. Based on prior data from our lab evaluating collagen alignment and

collagenase activity in primates with mild versus no prolapse,^{21,22} we estimate that 53 patients will have 99.6% power to detect a 48% difference between groups at the 2-sided 0.05 significance level.

Recruitment: Patients will be recruited from the Women's Center for Bladder and Pelvic Health, the Midlife Health Center, and Western PA Women's Healthcare Associates. Women will be approached for study participation if they have symptomatic mild (stage I-III) POP, as measured by POP-Q exam, ¹¹ and have chosen to proceed with PFPT for management. Inclusion/exclusion criteria are listed below.

Inclusion criteria:

- Women in good health aged 40-80
- Has symptoms of pelvic organ prolapse; answers "yes" to at least 1 of the following questions:
 - Do you feel or see a vaginal bulge?
 - Do you feel pressure in the vagina?
- Meets POP-Q criteria on exam for stage I, II, or III prolapse
- Interested in PFPT for management of POP
- Normal mammogram within 1 year of enrollment

Exclusion criteria:

- Prior surgery for prolapse
- Other prior interventions for prolapse (e.g. pessary, PFPT)
- Connective tissue diseases known to affect collagen or elastin remodeling
- Known liver dysfunction
- Unevaluated abnormal vaginal bleeding or abnormal pap smear in the previous year
- BMI > 35 kg/m^2
- History of estrogen therapy (including birth control) in the previous year
- Current or prior breast or pelvic malignancy (ovarian, tubal, uterine, cervical or vaginal)
- Contraindication to hormone use (e.g. thromboembolic disorder, use of anti-coagulants, coronary artery disease, history of stroke)

Interventions - Baseline Visit:

- I. Demographic data will be abstracted from the medical record by the research staff. Research variables include: age, race, ethnicity, BMI, age at menarche, history of oral contraceptive use, gravidity, parity, vaginal parity, number of cesarean sections, age at first full term pregnancy, age at last full term pregnancy, weight of largest baby, date of last/final menstrual period, age at menopause, time since menopause, current medications, smoking status, bowel habits, questions related to urinary and fecal incontinence, medical comorbidities (obesity, diabetes, chronic lung disease, constipation and irritable bowel syndrome), and surgical history (focusing on abdominopelvic surgeries and hernia repairs).
- II. All subjects will complete self-administered questionnaires. Pelvic floor symptoms will be assessed with the Pelvic Floor Distress Inventory (PFDI-20).²³ Sexual activity will be evaluated with the Pelvic Organ Prolapse Urinary Incontinence Sexual Questionnaire (PISQ-12).²⁴ Impact on quality of life will be measured with the Pelvic Floor Impact Questionnaire (PFIQ-7).²³ All of these questionnaires have been validated in women with pelvic organ prolapse.
- III. POP-Q exam, as described by the International Continence Society, is performed on all patients at their initial visit to the Women's Center for Bladder and Pelvic Health. As stated in the inclusion criteria above, only those patients who have stage I, II, or III prolapse on POP-Q exam will be approached for study participation.
- IV. A vaginal maturation index will be obtained on all patients in order to assess baseline estrogen status.

- V. Vaginal swabs will be collected from the posterior fornix for biochemical analysis. The vaginal swabs will be sent to [name] laboratory where collagenase activity will be measured.
- VI. Subjects will be randomized to receive either PFPT plus vaginal estrogen or placebo. A random allocation sequence will be achieved by generating a random number list using a computer.
- VII. Subjects will be given a 6 month supply of either vaginal estrogen or placebo and instructed on proper use (1 gram every night for 7 days, then 1 gram twice weekly thereafter for a total duration of 6 months). Handouts will be given which include these instructions and the potential side effects of vaginal estrogen therapy. The dose of hormones used in this study is the same as what we commonly prescribe in our office during routine clinical care. Several trials have evaluated the safety of vaginally delivered estrogen and reports of endometrial hyperplasia or cancer are rare. ²⁵⁻³⁰

VIII. All patients will be referred to the UPMC Centers for Rehab Services for PFPT for a treatment duration of 6 months. All women will undergo the standard PFPT program used in the treatment of prolapse. This includes weekly sessions for the first 4 weeks, followed by 1 session per month thereafter, with instructions for home practice.

Interventions – Follow-up:

- I. Phone call at 3 months: Subjects will receive a phone call from the research staff at 3 months following the initial baseline visit to assess compliance with therapy and to address questions.
- II. Follow-up visit at 6 months: Patients will be seen at the Women's Center for Bladder and Pelvic Health 6 months after initiation of therapy. The following activities will take place:
 - a. Questionnaire completion: Subjects will complete the same 3 questionnaires that they completed at their baseline visit (PFDI-20,²³ PISQ-12,²⁴ and PFIQ-7 ²³). The Patient Global Impression of Improvement questionnaire (PGI-I) will also be completed, which is a global assessment tool that has been validated in women undergoing treatment for prolapse.¹⁰
 - b. Patients will be asked to complete a brief confidential survey about the number of PFPT visits that they attended and the reason for any PFPT visits that were missed. This survey will also ask about vaginal symptoms over the course of the study, and about compliance with study drug therapy. In order to maintain blinding of the research staff, patients will fill out this survey in private and will place it in a sealed envelope when finished.
 - c. POP-Q examination will be performed
 - d. Vaginal maturation index and vaginal swabs for biochemical analysis will be collected

Primary outcome: Global impression of improvement with treatment, as measured by the PGI-I¹⁰

Secondary outcomes:

- Pelvic floor symptoms as measured by the PFDI-20 ²³
- Sexual complaints as measured by the PISQ-12 ²⁴
- Impact on quality of life as measured by the PFIQ-7²³
- POP-Q stage
- Biochemical markers collagenase activity

Data analysis:

Baseline characteristics will be analyzed using chi-square, Student's t-, or Mann-Whitney U test, as appropriate. Paired Student's t-test or Wilcoxon signed-rank test will be used to compare baseline and 6-month questionnaire scores, biochemical endpoints, and POP-Q measurements, as appropriate based on the distributions of the data. Student's t- or Mann-Whitney U test will be used to compare the change between the baseline and 6-month measurements between groups. Pearson's correlation coefficient and multivariable linear regression models will be used to examine the associations between clinical and biochemical outcomes. Statistical tests will be evaluated at the 0.05 significance level.

Safety Monitoring:

The risks associated with the use of vaginal estrogen are small, ²⁵⁻³⁰ and in this study, patients will be on hormones for only 6 months. Patients will be instructed to contact the research team in the event of any symptoms, such as breast tenderness, perineal pain, vaginal discharge, or bleeding. Persistent breast or perineal pain may require a decrease in the frequency of vaginal estrogen use. All bleeding will be evaluated by standard clinical guidelines. Several trials have evaluated the safety of vaginally delivered estrogen and reports of endometrial hyperplasia or cancer are rare. ²⁵⁻³⁰ At the discretion of the investigators, if continued study participation is felt to be unsafe for any woman, she will be withdrawn from the study. Drs. [name] and [name] will be responsible for monitoring for adverse events and side effects. Formal monitoring will take place at monthly research meetings which the investigators attend. Informal monitoring will occur more frequently and will be based upon need. All deviations from the normal course will be reported to the IRB.

Subject compensation:

Subjects will be provided with enough vaginal medication for the 6-month study duration. Study subjects will be compensated \$50 at their baseline visit and \$50 at their 6-month follow-up visit, for a total of \$100. Patients will also be reimbursed \$25 for each PFPT session attended, up to 9 sessions (for a total of \$225). A grant has been received from the American Urogynecologic Society which will cover the cost of this compensation.

Timetable:

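### Entry is open to women who still make estrogen, and the estrogen status measured at baseline is used neither in randomisation nor in the comparison of arms

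*Combined protocol and SAP*

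**What the plan says.** Under Recruitment, the only age or reproductive limit among the inclusion criteria is "Women in good health aged 40-80". The nearest exclusion is "History of estrogen therapy (including birth control) in the previous year". It concerns estrogen taken as treatment, not estrogen the woman makes. Neither list mentions menopause, ovarian status or pregnancy.

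The human tissue evidence in Background is a menopausal contrast: biopsies "in postmenopausal women who were not on hormones showed a decrease in type I collagen and collagen ratios compared to biopsies from premenopausal women", with no such decrease in postmenopausal women on hormones. The primate evidence cited there comes from ovariectomized animals.

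Estrogen status is recorded. Item I of the Baseline Visit lists "date of last/final menstrual period, age at menopause, time since menopause", and item IV states: "A vaginal maturation index will be obtained on all patients in order to assess baseline estrogen status". The index is repeated at 6 months.

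None of this is carried forward. Item VI describes the allocation as follows: "A random allocation sequence will be achieved by generating a random number list using a computer". No stratification is stated. In Data analysis the between-arm rule is "Student's t- or Mann-Whitney U test will be used to compare the change between the baseline and 6-month measurements between groups", with no stratum, covariate or subgroup for menopausal or estrogen status.

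**The concern.** The three aims ask what vaginal estrogen adds to pelvic floor physical therapy. On the deficiency part of the rationale, a woman with working ovaries has less deficit to correct, so she may contribute less to the contrast. Each such woman would then lower the average difference in PGI-I, POP-Q and collagenase activity.

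The Sample size section says the data are to be the foundation for a larger trial. If the effect varies with estrogen status, one pooled estimate is a poor guide to sizing that trial, and a null result would be hard to interpret unless the analysis took that status into account. With 53 women and an unstratified list, the arms can also differ in menopausal mix by chance.

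Separately, study estrogen is given for 6 months to women from age 40, and the eligibility text is silent on pregnancy.

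**Working it through.** **The plan's own figure.** The Sample size section states 99.6% power for a 48% difference with 53 women, two-sided 0.05. No standard deviation or rates are given, so it can be neither confirmed nor refuted. Read as a difference in means, 27 v 26, it needs a standardised difference of 1.29, that is an SD of 48/1.29 = 37%. It rests on primate collagen and collagenase data, not on the PGI-I.

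**Inputs.** From the documents: 27 v 26, two-sided 0.05. Assumed, because the documents do not give them:
- premenopausal share p: 10% to 40%;
- effect in those women: nil, or half of that in postmenopausal women;
- benchmark effect in postmenopausal women: d = 0.785, which 27 v 26 detects with 80% power.

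**Method.** Two-sample t-test, df = 27 + 26 − 2 = 51, noncentrality = d/√(1/27 + 1/26) = d/0.2748. At d = 0.785 this is 2.86 and power is 80%. The average effect is d(1 − p) under nil effect and d(1 − p/2) under half effect, with the SD held fixed. For the ordinal PGI-I this is an approximation.

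| p | Nil: d | Nil: power | Half: d | Half: power |
|---|---|---|---|---|
| 10% | 0.706 | 71% | 0.745 | 76% |
| 20% | 0.628 | 61% | 0.706 | 71% |
| 30% | 0.549 | 50% | 0.667 | 66% |
| 40% | 0.471 | 39% | 0.628 | 61% |

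Under nil effect the information is that of 53(1 − p)² women: 43, 34, 26 and 19 for the four shares.

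**Sensitivity to the benchmark.** At the standardised difference of 1.29 implied by the stated power, nil effect in premenopausal women leaves power of 98.6%, 95.8%, 89.8% and 79.0% for the same shares. The loss matters for moderate effects and much less for very large ones.

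**Chance imbalance.** With K of 53 women premenopausal and a 27/26 split, the number in one arm is hypergeometric. The probability that the arms differ by 15 percentage points or more in menopausal status is 24% for K = 16, 14% for K = 8 and 5% for K = 5.

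**Postmenopausal women only.** At p = 30%, 53 × 0.7 ≈ 37 women remain. Split 19 v 18, power at d = 0.785 is 64%. All 53 give 50% under nil effect and 66% under half effect, so the smaller subset wins clearly in the first case and loses slightly in the second.

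**The case against.** The strongest reply is that the mixed population is the intended one. Specific Aims and Background describe the clinic's practice of offering physical therapy with vaginal estrogen for mild symptomatic prolapse, with no menopausal limit. The rationale also includes estrogen receptors throughout the pelvic floor and animal data applied to women with normal support or mild prolapse. An average effect over the women offered this care is a legitimate target. This stands, and it is why a postmenopausal restriction cannot be called a required correction.

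The reply also notes that the data to look at effect by estrogen status are collected and that 53 is a budget-driven pilot sample. Both are true. But the plan does not say that these data will be used, and planning a larger trial is where they would help most.

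A reader might infer several stronger things that the documents do not support:
- **That dilution is a fact.** It needs both a real premenopausal share and a smaller effect in those women. The documents give neither.
- **That the comparison is biased.** Randomisation protects it. Chance imbalance adds noise, and no prognostic effect of menopausal status is shown.
- **That menstruating women are expected in number.** The recorded variables and the birth-control exclusion show that status may vary, not how many such women will enrol.
- **That pregnant women would be enrolled.** The protocol is silent, but it reports IRB approval, consent material is not in the public text, and other contraception or sterilisation is not ruled out.

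**Conclusion.** The point holds as a missed use of baseline information, together with a gap between eligibility and rationale that the plan does not explain. The criteria permit estrogen-replete women; the plan measures that status and then ignores it in allocation and in the tests.

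The possible cost is a fall from 80% power to between 71% and 39% (nil effect) or between 76% and 61% (half effect), for an assumed premenopausal share of 10% to 40% and an assumed d of 0.785. The direction requires only that the effect be smaller in women who make estrogen. The size cannot be fixed from the documents and could be small if few such women enrol. A null result would be less informative, but not unreadable, since status is recorded.

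The silence on pregnancy is a separate matter of reconciling the text.

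**What to change.** 1. **Baseline Visit, item VI:** generate the computer list separately for pre- and postmenopausal women, classified from the menstrual and surgical history already abstracted. Use permuted blocks within each list, because two unrestricted lists would not secure balance.
2. **Data analysis:** pre-specify the between-arm comparison in all 53 women, either stratified by menopausal status or adjusted for it or for the baseline maturation index. For outcomes that would go to a Mann-Whitney test, the van Elteren test is the stratified form. Report the postmenopausal estimate with its confidence interval alongside, for planning the larger trial.
3. **Recruitment:** state whether the target is all women offered this care or postmenopausal women. Restricting entry is the sponsor's option; it would narrow recruitment and the match to the practice described.
4. **Eligibility:** reconcile the absence of any pregnancy criterion with 6 months of study estrogen from age 40.

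The cost is a second list and slightly more analysis, with no patients lost. The postmenopausal-only estimate is less precise (about 37 women and 64% power at a 30% premenopausal share and d = 0.785), so it should accompany the analysis of all 53, not replace it.

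### The primary PGI-I comparison leaves chance imbalance in POP-Q stage uncorrected: no blocking or stratification is described, and no stage-adjusted analysis is planned

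*Combined protocol and SAP*

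**What the plan says.** - **Arm sizes** (Sample size): "A convenience sample size of 53 patients (27 in the treatment group and 26 controls) was chosen to comply with the budget".
- **Allocation** (Interventions - Baseline Visit, item VI): "A random allocation sequence will be achieved by generating a random number list using a computer". Ratio, blocks and strata are not mentioned here or elsewhere.
- **Population** (Specific Aims, Aim 1): "women with symptomatic stage I-III pelvic organ prolapse who are undergoing pelvic floor physical therapy". The matching inclusion criterion is "Meets POP-Q criteria on exam for stage I, II, or III prolapse". The mix of stages is not given.
- **Stage data** (Specific Aims, Aim 2): "POP-Q exam will be performed at baseline and 6 months after treatment". Baseline Visit, item III, makes the same exam a condition for being approached, so stage is on file before randomisation. PFDI-20 is also taken at baseline.
- **Primary outcome** (Interventions - Follow-up, item II.a): PGI-I is listed at the 6-month visit only.
- **Analysis** (Data analysis): the arms are compared by Student's t or Mann-Whitney U test, in a sentence worded for change from baseline. No covariate is named. Multivariable regression is reserved for relating clinical to biochemical results.

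**The concern.** Stage is a natural candidate for predicting how a woman rates her improvement, and the plan uses it in neither place where it could help. Allocation is not described as balancing it, and the primary comparison is not described as adjusting for it. With 53 women, a sizeable difference in stage mix between arms would not be unusual.

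Two things are at stake. The first is precision in a trial whose size is capped by budget. The second is how the result reads: if the arms do differ in stage, an adjustment chosen after seeing the data is open to challenge, and this pilot is meant to be the foundation for a larger trial. A smaller matter is that the planned 27/26 split is stated without a method that would secure it.

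**Working it through.** **1. The plan's own figures.** 27 + 26 = 53. The power statement ("we estimate that 53 patients will have 99.6% power to detect a 48% difference between groups at the 2-sided 0.05 significance level") rests on data such as "collagenase activity in primates with mild versus no prolapse", not on PGI-I. It gives no SD or rates, so it cannot be reproduced. Working backwards, a two-sided t-test at 27/26 reaches 99.6% at a standardised difference of about 1.29 (1.27 by normal approximation).

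**2. Arm sizes, if the list is simple 1:1.** The number on estrogen is Binomial(53, 0.5).
- P(exactly 27 on estrogen) = C(53,27)/2^53 = 10.8%
- P(27/26 either way) = 2 × 10.8% = 21.6%
- P(31/22 or more unequal) = 27.2%
- P(33/20 or more unequal) = 9.8%

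**3. Power cost of unequal arms.** Noncentral t with 51 df and noncentrality d/√(1/n1 + 1/n2):

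| Split | d = 0.8 (assumed) | d = 1.29 (step 1) |
|---|---|---|
| 27/26 | 81.5% | 99.6% |
| 31/22 | 80.4% | 99.5% |
| 33/20 | 79.1% | 99.4% |

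The loss is small.

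**4. Stage imbalance.** Let q be the stage III share, assumed 25% (range 15-35%). The SE of the between-arm difference in share is √[q(1−q)(1/27 + 1/26)] = √(0.1875 × 0.0755) = 0.119. A 15-point gap is 0.15/0.119 = 1.26 SE, with two-sided probability about 21%. Simulated simple allocations give:
- gap of at least 15 points: 21% (13-26% over the range of q)
- gap of at least 20 points: about 10% (4-13%)

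Fixing the list at 27/26 without strata does not help. For a stage making up 20-50% of women, a gap of at least 15 points has probability 18-28%, against 20-27% with a simple list.

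**5. Precision lost by ignoring stage.** Suppose stage III differs on PGI-I by d within-stage SDs (assumed 0.5-1.0). Then R² = q(1−q)d²/[1 + q(1−q)d²], and the equivalent sample size is 53/(1−R²) = 53 × [1 + q(1−q)d²].
- d = 0.5: 53 × 1.0469 = 55.5, about 2 extra women
- d = 1.0: 53 × 1.1875 = 62.9, about 10 extra women

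This treats the outcome as continuous, so it is a guide for an ordinal scale.

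**6. Effect within one unbalanced trial.** A 20-point gap with d = 0.8 moves the contrast by 0.20 × 0.8 = 0.16 SD. The SE at 27/26 is √0.0755 = 0.275, so the shift is 0.58 SE. The unadjusted test uses a total SD of √(1 + 0.1875 × 0.64) = 1.058 and rejects beyond 1.96 × 0.275 × 1.058 = 0.570. Its two-sided error, given that gap, is P(Z > (0.570 − 0.16)/0.275) + P(Z < −(0.570 + 0.16)/0.275), about 7% (6-8% for d = 0.5-1.0). Over all randomisations it does not exceed 5%.

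**7. What adjustment recovers.** One simulation assumed a 20/60/20 stage mix, a full SD of outcome per stage (a strong assumption) and no true effect. In trials with a mean stage gap above 0.2, the unadjusted estimate was off by 0.31 SD on average, and the stage-adjusted estimate by about zero. Over all trials the SE fell from 0.33 to 0.28.

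**8. What stratified blocks achieve.** In simulations with each stage as its own stratum, blocks of 4 and assumed mixes of 10/33/10, 5/38/10 and 15/28/10, no stage share differed by more than 11 points, and 27/26 occurred in 72-83% of trials. With two strata and blocks of at most 4, each stratum ends within 2. Since 53 is odd, one stratum has an odd count and ends within 1, so the arms differ by at most 2 + 1 = 3 (28/25). Example: 14 stage III women split 8/6 and 39 others split 19/20 give 8/27 − 6/26 = 29.6% − 23.1%, a gap of 6.6 points.

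**The case against.** The strongest reply is that the text is silent rather than wrong, and that little is lost. Four stronger readings are tempting, and the documents support none of them.

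- **That the list cannot deliver 27/26.** The protocol does not say the list is simple. A computer can produce a blocked list or one fixed at 27/26. The 21.6% is conditional on simple randomisation, and step 3 shows that missing the split matters little.
- **That PGI-I, having no baseline value, cannot be corrected for stage.** PGI-I is a rating of improvement, so no baseline score is expected. Baseline POP-Q stage is what corrects a stage imbalance, and every woman has it.
- **That the protocol itself expects benefit to fall from stage I to stage III.** The Background says "We do not suggest this treatment regimen for women with more severe prolapse, as we believe that it will have little clinical benefit", but Specific Aims and Recruitment label the whole of stages I-III as mild. On that usage the sentence concerns women outside the trial and shows no gradient within it.
- **That imbalance could manufacture or mask an estrogen effect.** Randomisation keeps the test valid on average. Step 6 puts the error at about 7% even given a 20-point gap, which itself arises in about 10% of trials.

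It can also be said that this is a declared pilot with a convenience sample, and that age (40-80) or baseline estrogen status, measured by the vaginal maturation index, has as good a claim to be a stratification factor. That is fair: the documents do not show that stage is the best choice. What stands is that the plan uses no baseline factor at all in the primary comparison, while stage defines eligibility, is known in advance and costs nothing to use.

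**Conclusion.** The point holds as one of precision and pre-specification, not of bias. Stage is neither described as balanced by design nor adjusted for in the primary comparison. An adjusted comparison backed by stratified blocks is a better method than the unadjusted test, using data already collected.

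The gain is modest: about 2 to 10 women's worth of information in 53, at 25% stage III and a stage difference of 0.5-1.0 SD. Both inputs are assumptions. The documents give neither the stage mix nor any relation between stage and PGI-I; if stage were unrelated to PGI-I, the gain would be nil. The missing block description is a lesser matter, because unequal arms cost about 2 percentage points of power even at 33/20 (81.5% to 79.1% at d = 0.8).

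**What to change.** - **Data analysis:** name the primary between-arm comparison of 6-month PGI-I explicitly, and adjust it for baseline POP-Q stage in two groups (I-II versus III), by ordinal logistic regression with stage as covariate or by a van Elteren test stratified by stage.
- **Interventions - Baseline Visit, item VI:** state that the 1:1 list is generated in permuted blocks of randomly varying size, at most 4, stratified by the same two groups. If another form of restriction was intended, describe it.

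**Cost:** one degree of freedom, two short lists instead of one, and a few sentences. Unfilled blocks can leave a difference of up to 2 within a stratum, so the plan should present 27/26 as a target. With ordinal regression the odds ratio is conditional on stage and should be reported as such. If allocation is already complete, only the analysis change remains available; it should be fixed before unblinding.
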